Tertiary outcomes. Patients and caregivers will report their physical and mental healthcare use in five domains (e.g., ER visits, outpatient visits) in the past 3 months at baseline and over the study period.^{59, 60} These reports of healthcare use were sensitive to change in an R01-funded cancer trial.⁶¹ At all time points, participants will also report whether professionals referred them to support services and whether referred services were received.^{52, 62} At all time points, participants will also report current medications using established methods from prior trials.^{63, 64} We will compute the total number of medications at each time point, as this variable had strong predictive validity for both healthcare use and costs in older adults over a 1-year period.⁶⁵

Measures of symptom severity. Symptom severity will be assessed to characterize the sample. For both patients and caregivers, fatigue severity and frequency will be measured with six items from the FSI,^{36, 37} and sleep disturbance, cognitive symptoms, anxiety, and depressive symptoms will each be assessed with an 6-item PROMIS measure.^{40, 41, 49, 57, 58, 66} Patients will also complete 3-item and 4-item PROMIS measures of pain severity and impact on functioning, respectively.⁵⁸

ACT Intervention Procedures

Drs. [name] and [name] developed the ACT manual (see Table 3 and Appendix K), which was informed by literature on the experiences of advanced GI cancer patients and caregivers,^{2, 3, 15, 67, 68} the ACT model,^{24, 35} previous ACT trials with cancer patients and other populations with physical and mental health conditions,^{25, 26, 29, 31, 33, 34} and [name] extensive experience delivering ACT to cancer patients and caregivers. A licensed therapist will deliver the intervention. While the therapist will aim to hold sessions on a weekly basis for 6 weeks, participants will have up to 12 weeks to complete the 6 sessions. Patients and caregivers will complete sessions 1 and 4-6 together via speakerphone. Sessions 2 and 3 will be delivered to patients and caregivers separately. Holding both dyadic and individual sessions will allow the therapist to meet the shared and unique needs of patients and caregivers. We adapted ACT to the dyad by incorporating joint mindfulness practices and leveraging the relationship during discussions. For example, participants will discuss moments of emotional connection with each

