Aim 2. Given that this is a pilot study, our data analytic approach for Aim #2 will be to derive effect size estimates rather than test for statistical significance. A linear mixed-model repeated measures approach (SAS Proc-Mixed) will be used to examine ACT's effects on primary and secondary outcomes. For outcome measures that only patients or caregivers complete (e.g., patient fatigue interference or caregiver burden), models will include main effects of time (as categorical) and study group and the time-by-study group interaction. Treatment effects will be evidenced by the interaction between time and study group (i.e., group mean differences after the intervention but no such differences at baseline). Models will include random intercepts to account for nonindependence of individuals' scores across time. For outcomes reported by patients and caregivers (e.g., psychological flexibility), multilevel modeling for dyadic data will be used.^{83, 84} Models will include the main effects of time, study group, and social role (patient vs. caregiver) as well as all two and three-way interactions between these variables. The time x study group x role interaction will estimate the degree to which treatment effects are different for patients and caregivers. Dyadic models will include random intercepts for patients and caregivers, as well as the covariance between the intercepts to account for nonindependence across time and across partners.

Aim 3. To conduct data analyses for Aim #3, we will use logistic and Poisson regression models to explore the effects of ACT on patient and caregiver physical and mental health service use (e.g., number of patient ER visits, patient and caregiver use of counseling and/or psychiatric medication). Logistic and Poisson regression analyses are appropriate for binary and count outcome data, respectively. Analyses will examine study condition as a predictor of health service use over the entire study period, controlling for baseline service use. Support service referrals will be a covariate in analyses of mental health service use.

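### The dyadic models tie partners together only through correlated random intercepts, so intervals for the role-averaged and role-difference treatment effects are miscalibrated if partners' visit-specific deviations correlate

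*Combined protocol and SAP*

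**What the plan says.** Section 11.0, Aim 2, names SAS Proc-Mixed and uses two kinds of model. Outcomes completed by one partner only, which include both primary outcomes, get a model with time, group, their interaction and a random intercept. For the rest, "For outcomes reported by patients and caregivers (e.g., psychological flexibility), multilevel modeling for dyadic data will be used". The fixed effects are full: "Models will include the main effects of time, study group, and social role (patient vs. caregiver) as well as all two and three-way interactions". One term is given a specific job: "The time x study group x role interaction will estimate the degree to which treatment effects are different for patients and caregivers".

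The dependence structure takes one sentence: a random intercept for each role, "as well as the covariance between the intercepts to account for nonindependence across time and across partners". The section does not mention the residual covariance, either to include a same-visit link between partners or to rule one out.

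The only outcome named as dyadic is psychological flexibility, as an example. From section 3.2 and Table 2, engagement in daily activities and value progress also use the same instrument in both roles. Quality of life uses different instruments, so I do not count it here. The stated aim is estimation: "our data analytic approach for Aim #2 will be to derive effect size estimates rather than test for statistical significance".

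**The concern.** The plan presents the intercept covariance as sufficient for dependence between partners. It is not. A random intercept describes how a person differs from the mean at every visit, so correlated intercepts say that partners are alike on average over the study. They do not allow partners to be up or down together at a particular visit. The stated model forces a patient's score to correlate with the caregiver's equally at the same visit and at different visits.

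Shared visit-level variation is plausible in this trial. Partners live through the same cancer course, and of the six ACT sessions, "Patients and caregivers will complete sessions 1 and 4-6 together via speakerphone"; the education/support arm has the same pattern. Both partners' follow-ups are timed from the last session.

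At stake are the confidence intervals around two quantities from the dyadic models: the treatment effect averaged over roles, and the difference in effect between patients and caregivers. Section 2.0 says that the findings will inform an application for a large trial, and intervals that are too narrow or too wide would mislead that planning.

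**Working it through.** The plan gives no figure for this point. Its one nearby figure, 80% power for d = .99 with 34 patients or 34 caregivers, reproduces: a two-sample noncentral t calculation with 17 per arm gives 0.799. It concerns the primary outcomes and does not enter below.

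**Inputs from the documents.** Two roles, three occasions, 50 dyads allocated 1:1, correlated role-specific intercepts (sections 3.0, 6.0 and 11.0). **Assumptions.** Equal residual variance s² in both roles, same-visit residual correlation r, and residuals independent across visits. The documents do not give r, so it is varied.

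**Step 1: intercepts cancel.** A person's change from baseline is (u + e1) − (u + e0) = e1 − e0. Its variance is 2s². The covariance between the two partners' changes is 2rs², whatever the intercept covariance.

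**Step 2: variance per dyad of the change contrasts.**
- One role: 2s². No r appears.
- Average of the two roles: (2s² + 2s² + 4rs²)/4 = s²(1 + r).
- Difference between roles: 2s² + 2s² − 4rs² = 4s²(1 − r).

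With independent residuals, the last two become s² and 4s². The ratios of model standard error to true standard error are therefore 1 (single role), 1/√(1 + r) (average) and 1/√(1 − r) (difference).

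| r | Single role | Role-averaged | Three-way |
|---|---|---|---|
| 0 | 1.00 | 1.00 | 1.00 |
| .1 | 1.00 | 0.95 | 1.05 |
| .2 | 1.00 | 0.91 | 1.12 |
| .3 | 1.00 | 0.88 | 1.20 |
| .4 | 1.00 | 0.85 | 1.29 |
| .5 | 1.00 | 0.82 | 1.41 |

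At r = −.1 the last two ratios swap, to 1.05 and 0.95.

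**Step 3: in standard-error units.** Take total variance 1 and s² = .5 (an assumed intraclass correlation of .5), 25 dyads per arm and r = .3. The role-averaged effect has a true SE of √(.5 × 1.3 × 2/25) = .228, against √(.5 × 2/25) = .200 from the model. The three-way effect has a true SE of √(4 × .5 × .7 × 2/25) = .335, against √(4 × .5 × 2/25) = .400.

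**Step 4: interval coverage.** By normal approximation, a nominal 95% interval covers 2Φ(1.96 × ratio) − 1. For the role-averaged effect this is 91% at r = .3 and 89% at r = .5. For the three-way effect it is about 98% and 99%.

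**Step 5: what the model implies for same-visit scores.** Add an assumed intercept correlation of .4. The true same-visit correlation is .5 × .4 + .5 × .3 = .35. The best-fitting intercept covariance absorbs one third of the residual covariance (three occasions), so the fitted value is .20 + .15/3 = .25.

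**Step 6: simulation.** 250 trials of 50 dyads under the same assumptions were fitted by REML with and without the residual covariance. The effect examined was the change from baseline to the first follow-up. Ratios of mean SE, without to with:

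| Data | Patient | Caregiver | Role-averaged | Three-way |
|---|---|---|---|---|
| Complete | 1.00 | 1.00 | 0.88 | 1.20 |
| 15% of dyads lost before the first follow-up, 10% more before the second | 1.00 | 1.00 | 0.88 | 1.19 |

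With complete data the point estimates were identical. With dropout they differed by at most 0.06 standard deviations in any trial. The dropout runs used REML on the observed data, not the plan's multiple imputation.

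**The case against.** The strongest reply is that the plan is silent on the residual structure. It lists what the models will include and cites dyadic-modelling texts, so an analyst could add a same-visit covariance without breaking the plan. That is right as far as it goes. But the plan also says what its named terms achieve, and a Proc-Mixed fit with only those random effects and no REPEATED statement has independent residuals. Followed as written, the plan does not do what it claims.

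Second, the evidence for r is indirect. Assessments are individual phone calls with windows of −7 to +14 and −7 to +21 days, no rule says that partners are assessed together, and two of the six sessions are separate. The mean effect of joint sessions is absorbed by the fixed effects; only shared deviations from it matter. This stands, and r could be near zero or negative.

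Third, Aim 2 disclaims significance testing, the primary objective is feasibility and acceptability, and the primary outcomes are outside this model. The plan does not single out a role-averaged effect for reporting. This also stands and limits the weight of the point. It does not remove it, because an effect estimate still needs a sound interval and the plan does single out the three-way term.

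Three stronger readings are tempting, and the documents do not support them:
- **Same-visit scores are treated as independent.** They are correlated through the intercepts, and independent only conditionally on them.
- **All time-by-group standard errors are wrong.** The role-specific ones are not.
- **The trial's false-positive rate is inflated.** The plan sets estimation, not testing, as its aim, and the three-way interval errs on the wide side when r is positive.

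**Conclusion.** The point holds within narrow limits. For daily activities, value progress and psychological flexibility, the stated covariance structure represents only time-constant partner similarity. The consequence is confined to confidence intervals for the role-averaged effect, which are too narrow when r is positive, and for the role-difference effect, which are too wide. The sizes, 5% to 18% and 5% to 41% of the standard error, rest on an assumed r of .1 to .5, equal residual variances and a fit with no residual covariance.

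This is more than a missing detail, because the plan asserts that its structure is sufficient and relies on the three-way term for a stated purpose. It is a recommended correction and does not threaten the trial's primary conclusions.

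**What to change.** In the dyadic models, keep the role-specific correlated random intercepts (RANDOM with TYPE=UN, SUBJECT=dyad). Add a residual block linking the two roles within dyad and occasion: REPEATED role / TYPE=UN SUBJECT=dyad*time. Use Kenward-Roger degrees of freedom. State in section 11.0 that partner nonindependence is modelled at both the intercept and the occasion level, and report the estimated residual correlation, which is itself useful for planning the larger trial.

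The cost is one line of code and two extra covariance parameters (one if residual variances are held equal across roles), with no new data. For r of .1 to .5 the role-averaged interval widens by a factor of √(1 + r), about 5% to 22%. The three-way interval is multiplied by √(1 − r), so it narrows by about 5% to 29%.

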5.0 Study Design

The study procedures are shown in **Table 1**. Advanced GI cancer patients and caregivers ($N = 50$ dyads) who meet eligibility criteria and provide informed consent will be randomized to receive either six weekly sessions of the ACT intervention or the education/support condition. Outcomes will be assessed via telephone at baseline and approximately 2 weeks and 3 months post-intervention within the timing windows outlined below.

Table 1

Timing	Procedure and person(s) responsible
At least 3 weeks after the patient's advanced GI cancer diagnosis	
(1) The research assistant will contact potentially eligible patients, screen patients for eligibility, and obtain informed consent, which can be done verbally over the phone or face to face in the outpatient clinics at the IU Simon Cancer Center or Eskenazi Health (see "recruitment process" below).
 
(2) The research assistant will contact potentially eligible caregivers, screen caregivers for eligibility, and obtain informed consent, which can be done verbally over the phone or face to face in the outpatient clinics at the IU Simon Cancer Center or Eskenazi Health (see "recruitment procedures" below). If the caregiver is not eligible or does not consent to participate, then the patient will be informed that s/he is not eligible for the study.

Target date = about 1 week after recruitment of the patient and caregiver. The baseline assessment can be completed up to 1 month after recruitment.	(3) Patients and caregivers who consent to participate will complete a 30- or 25-minute baseline assessment over the phone, respectively (see "interview procedures" below). The interview will be administered by a trained research assistant or a trained doctoral student in clinical psychology.
Sessions will occur approximately 1 week from each other, with the first session occurring about 1 week following the baseline assessment. Participants will have up to 12 weeks to complete the 6 sessions.	(4) Patients and caregivers will participate in six, 50-minute telephone-based sessions of ACT or education/support. Sessions will be administered by licensed mental health professionals who are supervised by the PI and [name] who are clinical psychologists.

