Target date = approximately 2 weeks after the last intervention session. Assessments can be completed as early as 7 days prior to this target follow-up date or as late as 14 days following the target follow-up date.	(5) Patients and caregivers will complete a 30-minute assessment over the phone (see "interview procedures" below). Assessments will be administered by a trained research assistant or a trained doctoral student in clinical psychology who are blinded to the intervention arm.
Target date = within 2 weeks of the 2-week post-intervention assessment. The qualitative interview can be completed as early as the same day as the 2-week follow-up or as late as 21 days after the 2-week follow-up.	(6) Patients and caregivers in the ACT condition will complete a 30-minute qualitative phone interview on intervention acceptability. The interview will be administered by a trained doctoral student in clinical psychology.
Target date = approximately 3 months after the last intervention session. Assessments can be completed as early as 7 days prior to this target follow-up date or as late as 21 days following the target follow-up date.	(7) Patients and caregivers will complete a 25- or 20-minute assessment over the phone, respectively. Assessments will be administered by a trained research assistant or a trained doctoral student in clinical psychology who are blinded to the intervention arm.

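### Aim 3 puts service-use counts over unequal observation periods into plain Poisson regression, with no exposure offset and no allowance for overdispersion

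*Combined protocol and SAP*

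**What the plan says.** Section 11.0 (Aim 3) commits the service-use outcomes to two models: "we will use logistic and Poisson regression models to explore the effects of ACT on patient and caregiver physical and mental health service use". The ground given is that "Logistic and Poisson regression analyses are appropriate for binary and count outcome data, respectively". One example given is the "number of patient ER visits". The analysis is described this way: "Analyses will examine study condition as a predictor of health service use over the entire study period, controlling for baseline service use". Support-service referrals are added as a covariate for mental health use. Neither Aim 3 nor any other section mentions person-time, an offset, overdispersion, robust standard errors or a negative binomial model.

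The length of observation is set elsewhere:

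- Section 5.0 (Table 1) puts the first session about 1 week after baseline and adds "Participants will have up to 12 weeks to complete the 6 sessions". The 3-month assessment is dated from the last session and may fall 7 days early or "as late as 21 days following the target follow-up date".
- Section 10.0 ends participation for both members of a dyad if either dies, cannot continue or stops.
- Section 7.0 has participants report service use "in the past 3 months at baseline and over the study period".
- Section 11.0 applies multiple imputation with 50 samples to missing data. It gives no rule for service use after death or withdrawal.

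**The concern.** Plain Poisson regression assumes that the variance equals the mean and, without an offset, that everyone was observed for the same time. The plan's own schedule breaks the second assumption. The first is doubtful for visit counts in people with advanced cancer, where a few participants may account for many visits. When either fails, the model's standard errors can be too small. Unequal time also means that the fitted quantity is a ratio of mean counts over differing periods, not a rate ratio. Baseline use covers a fixed 3 months, so adjusting for it does not correct for time observed later.

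Section 2.0 says the findings will inform a larger trial application. The interval around a service-use ratio is therefore the part most likely to be carried forward.

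**Working it through.** The only power figure in the plan concerns the Aim 2 primary outcomes. Aim 3 has no stated event rate, dispersion or precision, so there is nothing to reproduce. Means, dispersion and exit patterns below are assumptions. The true ratio is 1 throughout.

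1. **Observation time for completers** (taking 3 months as 13 weeks and the 12-week limit from session 1).
   - Shortest: 1 week to session 1 + 5 weeks of weekly sessions + 13 − 1 = 18 weeks.
   - Longest: 1 + 12 + 13 + 3 = 29 weeks.
   - Ratio of the extremes: 29/18 = 1.6. These are window limits, not an expected spread.

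2. **Overdispersion, unadjusted.** With variance μ + kμ², the true standard error is √(1 + kμ) times the Poisson one. At k = 1 this is √2 = 1.41 for μ = 1 and √4 = 2.00 for μ = 3. Simulated coverage of the nominal 95% interval, 21 per arm, equal follow-up:

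| Mean μ | k = 0 | k = 0.5 | k = 1 | k = 2 |
|---|---|---|---|---|
| 0.5 | 95.7% | 93.2% | 90.5% | 85.6% |
| 1 | 95.5% | 89.6% | 84.3% | 75.4% |
| 3 | 95.1% | 78.7% | 67.9% | 54.3% |

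   Robust standard errors gave 92.2% to 95.1% over the same grid.

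3. **Overdispersion with the planned baseline adjustment.** Baseline use absorbs part of the stable variation between people. The setting is 21 per arm, k = 1, means of 1 to 3, and person-level rates that stay constant between a 13-week baseline and a follow-up of about 21 weeks. The interval wrongly excludes 1 in:
   - 11% to 17% of trials with log baseline count as covariate;
   - 12% to 22% with the raw baseline count;
   - about 7% with robust standard errors.

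   Unadjusted, the corresponding figures from step 2 are 100 − 84.3 = 15.7% at mean 1 and 100 − 67.9 = 32.1% at mean 3.

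4. **Unequal time alone.** Events are truly Poisson, 25 per arm, with the plan's windows. Leavers are observed for a uniform 10% to 100% of their period, with the same exit rate in both arms. The 21% rate mirrors the 79% retention at 12 weeks in the team's earlier pilot (section 1.0). The 30% rate is the most that the 70% completion criterion in section 11.0 tolerates. Coverage without an offset:

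| Early exit | Mean 1 | Mean 3 | Mean 5 | Mean 10 |
|---|---|---|---|---|
| 21% | 94.9% | 92.8% | 91.4% | 87.3% |
| 30% | 94.6% | 92.1% | 90.2% | 85.5% |

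   A log-time offset restored 95% to 96%. The loss is negligible for rare events and grows with frequency.

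5. **Bias in the ratio.** When time varied over 18 to 29 weeks equally in both arms, or 32% left early in each arm, the mean ratio without an offset was 1.00. Bias appears only with a difference between arms. Leavers contribute on average 0.55 of the period, so mean exposure at exit rate p is 1 − 0.45p:
   - 10% v 20%: 0.910/0.955 = 0.95
   - 15% v 30%: 0.865/0.9325 = 0.93
   - 20% v 40%: 0.820/0.910 = 0.90
   - mean session span 2 weeks longer in one arm: 21/19 = 1.11

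   In the three exit scenarios the offset returned the simulated ratio to 0.99 to 1.00.

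**The case against.** The strongest case against has five parts.

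- **No necessary bias.** A reader might infer that unequal follow-up biases the comparison by itself. The documents do not support this: allocation is randomised 1:1 and the session schedule is identical in both arms. Step 5 shows no bias unless time differs by arm, and nothing in the plan says that it will. This stands.
- **Dispersion is undocumented.** A reader might also infer that the intervals must be too narrow. With no overdispersion and equal follow-up, coverage was 95.1% to 95.7%. This stands, so the conclusion is conditional. Step 4 shows, however, that frequent events with early exit are enough without any further dispersion.
- **Baseline adjustment helps.** It does, and unadjusted figures overstate the problem. It does not remove it (step 3).
- **The recall wording is not visible.** The follow-up interviews are in appendices that are only listed. If the items use a fixed recall period, completers may have equal reported exposure. This limits the offset argument for completers, but not the effect of early exit or the dispersion point. Aim 3 does define its outcome over the entire study period.
- **Status of the aim.** It is exploratory, its outcomes are tertiary, and section 11.0 specifies neither a test nor an interval for it. This stands and lowers the priority.

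**Conclusion.** The point holds in conditional form. The plan fits plain Poisson models to counts gathered over periods that its own rules make unequal, and provides for neither exposure nor dispersion. If dispersion is about 1 and means are 1 to 3, the error rate of a nominal 95% interval is roughly 11% to 22% instead of 5% after baseline adjustment. If there is no extra dispersion but 21% leave early, coverage is about 93% at a mean of 3 and 87% at a mean of 10. Bias in the ratio requires observation time to differ between arms; it was 5% to 11% in the scenarios tried.

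The overdispersion argument does not extend to the binary outcomes analysed by logistic regression. All sizes rest on assumed rates, dispersion and exit patterns. Priority is low to moderate: no feasibility or acceptability criterion depends on Aim 3, but a better method is available at little cost.

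**What to change.** For count outcomes in Aim 3, specify Poisson regression with robust (sandwich) standard errors, or negative binomial regression, adjusted for baseline use. State the form in which baseline use enters, because the log and raw counts performed differently in step 3.

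Add as an offset the log of the time covered by completed service-use reports, from randomisation or baseline to the last completed interview. Do not run it to death or withdrawal. Use is self-reported, so time after the last interview adds exposure with no chance of a recorded event and understates the rate.

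Say how this fits with the multiple imputation. If use after withdrawal is imputed, the offset must cover the imputed period; if not, it stops at the last report. State how time after death is treated.

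The cost is a few sentences in section 11.0 and somewhat wider intervals. The offset needs interview dates, not dates of death, and section 8.0 already requires every participant contact to be documented. Two limits remain: with about 21 per arm, robust intervals still err in about 7% of trials, and an offset does not remove bias from informative death.
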